### 7. SAMPLE SIZE DETERMINATION

It is assumed that the proportion of subjects who achieve PGA score of clear (0) or almost clear (1) with a minimum 2-grade improvement from Baseline at Week 12 will be 40% for subjects receiving tapinarof compared with 15% for subjects receiving vehicle control. With 500 subjects randomized in a 2:1 ratio (approximately 333 subjects receiving tapinarof cream, 1% and approximately 167 subjects receiving vehicle cream) there will be > 99% power for statistical significance (2-sided p< 0.05). If tapinarof response rate is 35%, and vehicle response rate is 20%, the power will be > 94%. Power comes from a Fisher Exact sample size calculation which is conservative. It is assumed that up to 25% of the subjects will be lost to follow-up by 12 weeks. These subjects will be included in the primary analysis in the ITT population using the multiple imputation method as detailed below.

### 8. ANALYSIS POPULATIONS

The following populations are defined:

- Safety population: All randomized subjects who receive at least 1 application of study drug will be included in the Safety population. Subjects will be analyzed as treated.
- Intent-to-treat (ITT) population: All randomized subjects will be included in the Intent-to-treat population. Subjects will be analyzed as randomized.
- Per Protocol (PP) population: All subjects in the ITT population who did not have any major protocol deviations or other events that may impact the interpretation of the primary efficacy endpoint will be included in the PP population. Exclusion criteria for the PP Population may include:
  - o Failure to meet the enrollment inclusion/exclusion criteria
  - On-study use of oral corticosteroids for >3 days and/or at >10mg dose
  - Failure to have a Week 12 assessment that occurs <=3 days post last dose and also between study day 78 to 91 (inclusive) for the primary efficacy endpoint. Alternative days post dose and visit window may be used upon review of the actual blinded data before database lock.

• Failure to be compliant with treatment regimen (as defined in Section 12.4, i.e., compliance < 80%)

Additional criteria that may or may not be documented as protocol deviations may be added to determine PP population. The composition of the PP population will be determined and documented in blind reviews of the database conducted prior to unblinding the study database.

The ITT and PP Populations will be used for the analyses of efficacy endpoints. The ITT population is considered as the primary population for efficacy analyses and the PP will be considered as supportive. If a subject receives an incorrect study treatment other than the intended study treatment, the analysis of that subject's data will be based on the actual treatment received for the safety and PP analyses and the randomized assignment for the ITT analyses. If a subject receives more than 1 study treatment, the treatment group assignment for the safety and PP analyses will be determined on a case by case basis.

• Pharmacokinetic (PK) population: All subjects who undergo plasma PK sampling and have evaluable concentration-time data for analysis will be included in the PK population. A sample that is below the limit of quantification (BLQ) of the assay is considered evaluable.

### 9. HANDLING OF MISSING DATA

### Imputation of Start and End Dates of Adverse Event (AE)

To calculate duration of Adverse Events, the following rules will be used where applicable to impute partial or completely missing start dates or end dates:

- If only the day is missing for a start date, the 1st of the month will be imputed. If the new estimated date falls before the date of first dose, while the known month and year match the month and year of the first dose, the date of first dose will be used as the new estimated date. The AE will be considered as a treatment-emergent AE (TEAE).
- If only the day is missing for an end date, the last day of the month will be imputed. If the new estimated date falls after the date of last study visit, the date of last study visit will be used as the new estimated date. Last study visit is defined as the Week 12 visit for those who elect to participate in the open-label long-term study, or the Week 16 Follow-up visit for those who fail to qualify for participation in the open-label study, or who qualify to participate but ultimately elect not to enroll.
- If both the day and the month are missing for a start date or end date, no imputation will be used, and the duration will not be calculated. However, if the year of start is the same or greater than the year of the first dose date, the AE will be considered as treatment emergent.

• If the start date or end date is completely missing, duration will not be calculated. However, an event with completely missing start date will be considered as treatment emergent.

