## **6.3.** Safety Assessments

#### **6.3.1.** Adverse Events

All AEs will be collected from the time the subject signs the ICF until the final visit/contact with the subject. Additional safety information, including the definition of an AE and the methods for recording, evaluating, and assessing causality of AEs and the procedures for completing and transmitting SAE reports are provided in Section 8.

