## 7.1. Visit 1; Screening Period (Day -34 to Day -1)

After the subject has signed the Informed Consent Form (ICF), potential study subjects will undergo Screening procedures and assessments to confirm eligibility to participate in the study. Screening assessments will include the following:

- Demography recording
- Serum pregnancy test (females of child-bearing potential)
- Medical history recording
- ECG recording
- Brief physical examination (including weight, height, and body masss index [BMI])
- Vital signs measurements
- HADS assessment
- PGA score
- %BSA affected calculation; subject's scalp, palms, and soles should be excluded from the %BSA calculations used to determine patient's eligibility
- Blood sample collection for clinical laboratory tests (serum chemistry, hematology, diagnostic tests)
- Urinalysis
- AE recording (from the time the ICF is signed)
- Concomitant medication recording (from the time ICF is signed)

To determine subject eligibility at Screening, a single repeat of tests or procedures may be allowed at the discretion of the Investigator. The Medical Monitor should be consulted if needed.

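### The SAP's partial-date rules never check an adverse event's end date, so an event that ended before first dose can be counted as treatment-emergent, under one rule with an impossible duration

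*SAP*

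**What the plan says.** SAP Section 9 introduces its adverse event date rules with this purpose: "To calculate duration of Adverse Events, the following rules will be used where applicable to impute partial or completely missing start dates or end dates".

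There are three rules for start dates.

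- **Day missing.** "If only the day is missing for a start date, the 1 st of the month will be imputed". If the result is earlier than first dose, "while the known month and year match the month and year of the first dose", a second step applies: "the date of first dose will be used as the new estimated date. The AE will be considered as a treatment-emergent AE (TEAE".
- **Day and month missing.** Nothing is imputed and no duration is calculated, but the event is treatment-emergent if its start year is the first-dose year or later.
- **Completely missing.** No duration is calculated, but "an event with completely missing start date will be considered as treatment emergent".

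For end dates: "If only the day is missing for an end date, the last day of the month will be imputed", with the date of the last study visit as an upper limit. No rule compares the end date with first dose or with the imputed start.

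Protocol Section 6.3.1 sets the collection period: "All AEs will be collected from the time the subject signs the ICF until the final visit/contact with the subject". Protocol Section 7.1 gives the window before dosing: "Visit 1; Screening Period (Day -34 to Day -1". SAP Section 12.9.1 defines a treatment-emergent event as one that starts after the first dose.

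**The concern.** Treating an event of unknown timing as treatment-emergent is normal caution. Here the timing may be known. An event with a recorded end before first dose cannot have started after it, yet the day-missing rule says that it did.

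Two errors follow. An event from before treatment enters the treatment-emergent tables, contrary to the definition in SAP Section 12.9.1 and to the scope that Protocol Section 10.4.3 sets for adverse event summaries. Its imputed start also falls after its recorded end, so the rule fails at its stated purpose of supporting a duration.

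The outputs affected are the treatment-emergent counts, the listings that show onset and duration, and the displays for the adverse events of special interest (contact dermatitis, folliculitis, headache). For these, SAP Section 12.9.1 summarizes earliest onset day and maximum duration, and plots time to first event. An event from screening would appear there with onset on the first-dose date, which looks like an immediate reaction.

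The SAP uses the needed logic elsewhere. Section 12.5 separates prior from concomitant medications by stop date, including partial stop dates.

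**Working it through.** The plan gives no figure on this point to reproduce, so the check applies the rule as written.

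**Inputs**

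- Day-missing start rule and end-date rule: SAP Section 9.
- Collection from consent, Day -34 to Day -1: Protocol Sections 6.3.1 and 7.1.
- Duration: the SAP gives no formula for adverse events. Two forms are assumed: D0 = end - start, and D1 = end - start + 1. The SAP adds one day for days in study (Section 12.1) and days exposed (Section 12.4), but does not say so for adverse events.

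**1. Example.** First dose is 20 September; the event starts on an unknown day in September and ends on 10 September. The first step gives 1 September. This is before first dose and in the same month, so the start becomes 20 September and the event is treatment-emergent.

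- D0 = 10 - 20 = -10 days
- D1 = 10 - 20 + 1 = -9 days

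**2. General case.** Let first dose be day d of the month and the recorded end day e of the same month, with e < d. The imputed start is d.

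- D0 = e - d, which is at most -1, so always negative.
- D1 = e - d + 1, which is at most 0. It is zero only when the event ended the day before first dose (e = d - 1).

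**3. Enumeration.** A month of L days holds L(L - 1)/2 pairs with e < d. Over the 2019 calendar, used only as a calendar, the total is 7 × 465 + 4 × 435 + 1 × 378 = 5373 pairs.

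| Result under the rule | Pairs |
|---|---|
| Classed as treatment-emergent | 5373 of 5373 |
| D0 negative | 5373 (minimum 1 - 31 = -30) |
| D1 zero (e = d - 1) | 365 - 12 = 353 |
| D1 negative | 5373 - 353 = 5020 (minimum -29) |
| D1 positive | 0 |

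**4. Limits of the effect**

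- *End day also missing.* In the example the end becomes 30 September (if the last-visit limit does not apply), so D1 = 30 - 20 + 1 = 11. The duration is positive, and the recorded dates do not rule out onset after dosing.
- *Start month before the first-dose month.* The start stays at the 1st of that month and is not moved forward.
- *Day and month missing, or start completely missing.* A recorded end before first dose does not prevent the treatment-emergent label, but no duration is calculated.

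**5. What can be said about size.** If onsets of screening events were uniform over all 34 days, and first doses uniform over the year, the average share starting in the first-dose month would be 5373/(365 × 34) = 0.433, or 43%. By first-dose day the share runs from 0% (the 1st) to 30/34 = 88% (the 31st). Only those that also have a missing start day and a complete end date before first dose are affected by the day-missing rule. The documents give no rate for either.

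**6. Check of the fix.** Keeping the 1st of the month gives D1 = e - 1 + 1 = e, at least 1 day for all 5373 pairs, and D0 = e - 1, at least 0. None is treatment-emergent. In the example, the start is 1 September and D1 = 10 days. With a consent date on day c of the same month, c no later than e, D1 = e - c + 1, again at least 1.

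**The case against.** The strongest defence is deliberate caution. SAP Section 12.9.1 treats missing causality as related and missing severity as the highest level, and counting doubtful events as treatment-emergent fits that pattern. The same rule applies in both arms to events that precede treatment in a blinded, randomized trial, and safety data get no formal comparison, so no difference between arms is to be expected from it.

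The case should also be rare. A site would have to know exactly when a recent event ended but not the day it began. Protocol Section 9 provides for querying inconsistencies, and SAP Section 5 puts data review before lock. Duration is summarized only for events of special interest, by each subject's maximum, so an impossible value reaches that summary only if it is the subject's sole or longest episode.

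The points on rarity and on the comparison between arms stand. The defence from caution does not, because the end date already settles the timing. Data review does not cure the rule either: a partial start date with a complete end date is not itself inconsistent, and the contradiction appears only after imputation.

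A reader might infer that every event resolved before dosing becomes treatment-emergent with a negative duration. The documents do not support that. The impossible duration needs a missing start day, a start month equal to the first-dose month, and a complete end date before first dose, all together. A reader might also take the 43% as a misclassification rate. It is only the share of hypothetical screening events that start in the first-dose month. Nor do the documents show that headache is common during screening; they establish only that it is an event of special interest and was frequently reported in earlier tapinarof studies.

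**Conclusion.** The day-missing rule is wrong as written. Whenever the start month and year are those of first dose and a complete end date precedes first dose, it labels the event treatment-emergent against the SAP's own definition and gives a duration that cannot be true: always negative under D0, zero or negative under D1. That result depends only on the rule and on which of the two assumed formulas is used. The other two start-date rules share the missing end-date check, with misclassification as the only consequence.

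This is a minor point. The number of events is probably small and cannot be derived from the documents. The effect is confined to the safety outputs and does not reach any efficacy analysis.

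**What to change.** Amend SAP Section 9 in two places.

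1. In all three start-date rules, add: *unless the complete or partial end date shows that the event ended before the first dose, in which case the event is not treatment-emergent.* A partial end date can settle this when its month and year, or its year alone, precede those of first dose.
2. In the day-missing rule only, add for such events: *the imputed start remains the 1st of the month, or the consent date if that is later and in the same month, and is never later than the end date.* The other two rules create no start date, so they need no such sentence.

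Keep the treatment-emergent assignment for every event whose end date does not rule out onset after first dose. It would also help to state the adverse event duration formula.

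The cost is a few sentences in the SAP and a small change to the program that derives adverse event dates. No new data are needed, and caution for ambiguous dates is unchanged.

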#### **8.3.2.** Follow-Up of Adverse Events

After the initial AE/SAE report, the Investigator is required to proactively follow each subject at subsequent visits/contacts. All SAEs and nonserious AEs will be followed until resolution, until the condition stabilizes, until the event is otherwise explained, or until the subject is lost to follow-up.

The Investigator will assess the outcome of each AE using the following criteria:

- **Recovered/Resolved:** The event has improved or subject recuperated.
- Recovered/Resolved with sequelae: The subject has recuperated but retained pathological conditions resulting from the prior disease or injury.
- **Recovering/Resolving**: The event is improving.
- Not recovered/Not resolved: The event has not improved or subject recuperated.
- **Unknown**: The outcome of the event is not known, not observed, not recorded, or refused.
- **Fatal:** Termination of life as an outcome of the AE.

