At each level of summarization, a subject will be counted once if he/she reported one or more events. The severity of TEAEs and relationship to study drug will be summarized in a similar manner. For summaries of relationship to study drug, a subject will be classified according to the closest relationship. For summaries of TEAE CTCAE grade, a subject will be classified according to the worst grade.

For AESIs, summarization will be more extensive, reflecting the more detailed information collected. Information summarized will include number of events per subject, earliest onset day, duration (in days), causality, grade and seriousness of AESIs, outcome, actions taken with study drug, assorted physical characteristics of the AESIs, and demographic/baseline characteristics and PGA status of the subjects experiencing them. Each type of AESI will be summarized separately. If a subject has more than one treatment-emergent occurrence of an AESI, the subject's maximum duration, highest levels of causality and seriousness, maximum grade and generally the most extreme level of each characteristic will be summarized. If an AESI was ongoing at EOS, it will not be included in the duration summary.

A Kaplan-Meier figure will be generated for each AESI of time to first event. Subjects not experiencing the AESI will be censored at the date of study completion or discontinuation.

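### SAP 9 caps a day-missing AE end date at the last study visit without checking the recorded month, so a later recorded end month is overwritten and the duration shortened

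*SAP*

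**What the plan says.** SAP Section 9, under the heading on AE start and end dates, gives the purpose of the rules: "To calculate duration of Adverse Events, the following rules will be used where applicable". The parts that matter here are:

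- **End date, day missing, step 1.** "If only the day is missing for an end date, the last day of the month will be imputed".
- **End date, day missing, step 2.** "If the new estimated date falls after the date of last study visit, the date of last study visit will be used as the new" end date.
- **Start date, day missing.** The imputed date moves to the first-dose date only "while the known month and year match the month and year of the first dose".
- **Less information than that.** If day and month are both missing, or the whole date is missing, no duration is calculated.
- **Last study visit.** This "is defined as the Week 12 visit for those who elect to participate in the open-label long-term study". For those who do not qualify for that study, or qualify but do not enroll, it is the Week 16 follow-up visit.

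On follow-up, Protocol Section 8.3.2 states: "All SAEs and nonserious AEs will be followed until resolution, until the condition stabilizes, until the event is otherwise explained". On reporting, SAP Section 12.9.1 lists a duration for every AE and summarizes duration for the AESIs (contact dermatitis, folliculitis, headache), with this exclusion: "If an AESI was ongoing at EOS, it will not be included in the duration summary".

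**The concern.** A cap at the last visit is reasonable when the recorded end month is the visit month: the day is unknown, and the visit date is one of the days the record allows. When the recorded month is later, the rule no longer fills in a missing day. It replaces a month and year that the site did record with a date outside that month.

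The three possible states of knowledge are then treated inconsistently. A complete end date after the visit is kept, since the SAP states no cap for it. A date with only the year known gives no duration. A date with month and year known gives a duration that the record itself rules out. Two events that end on the same day after the visit can differ in reported duration only because one site left out the day.

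At stake is the accuracy of reported AE durations. Duration of TEAEs and SAEs is among the protocol's safety endpoints (Protocol Section 2), and the error always runs towards shorter events.

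**Working it through.** The plan states no figure to reproduce, so the check applies the rule literally.

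**Inputs.** The two end-date steps and the start-date condition come from SAP Section 9. Visit dates and onset dates are assumed. Duration is counted inclusively (end minus start plus 1). The SAP gives no formula for AE duration, so this is also an assumption, but the shortening in days does not depend on it.

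**Can such a date arise?** Three provisions make it possible. AEs are followed to resolution or stabilization. The last study visit for roll-over subjects is Week 12. SAP 12.9.1 includes a roll-over subject's AE by onset date, up to and including the Week 12 visit day, whatever its end date.

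**Worked example (assumed dates).** Onset 1 March 2020, last study visit 10 March 2020, end day missing.

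| Recorded end | End-of-month date | Date after cap | Duration under SAP | Duration the record allows | Duration with month-match condition |
|---|---|---|---|---|---|
| March 2020 | 31 March | 10 March | 10 days | 1 to 31 days | 10 days |
| April 2020 | 30 April | 10 March | 10 days | 32 to 61 days | 61 days |
| May 2020 | 31 May | 10 March | 10 days | 62 to 92 days | 92 days |

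For April, the lower bound is 31 + 1 = 32 and the upper bound is 31 + 30 = 61. A complete end date of 1 April would give 32 days, against 10 days if the same date were recorded only as April. The month-match condition takes the upper end of the allowed range, which is the SAP's existing end-of-month convention. In the March row it changes nothing.

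**Size of the shortening in general.** The shortening is the true end date minus the visit date. When the recorded month is the calendar month after the visit:

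- Smallest: visit on the last day of a month, event ends on the 1st of the next, 1 day.
- Largest: visit on the 1st of a 31-day month followed by another 31-day month (such as July and August), event ends on the last day, 30 + 31 = 61 days.

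This was enumerated over every visit date from 1 July 2019 to 30 June 2020 and every end day compatible with the recorded month, all weighted equally:

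| Recorded end month | Range of shortening | Mean | At least 7 days | At least 14 days |
|---|---|---|---|---|
| One month after visit month | 1 to 61 days | about 31 | 98% | 90% |
| Two months after visit month | 30 to 91 days | about 61 | 100% | 100% |

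In both rows the assigned date lies outside the recorded month every time. If the recorded month is the visit month and the event ended on or after the visit, the shortening is 0 to 30 days, but the assigned date stays consistent with the record.

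**The case against.** **Such dates may be rare or absent.** Protocol Section 8.3.1 collects AEs only until the final visit, and SAP Section 1 limits the plan to double-blind phase data. The documents do not say whether a resolution date after Week 12 for a roll-over subject enters this database. This stands as a limit on frequency. It does not justify the wording, because the follow-up provision allows for later end dates and the cap exists to handle imputed dates past the visit.

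**The reach is narrow.** Although duration of TEAEs and SAEs is a protocol endpoint, the SAP plans no duration summary for TEAEs or SAEs in general. Outside AESIs, the effect is one value in a by-subject listing for each affected event. This stands.

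**The AESI summary may be protected already.** A reader might infer that a capped AESI necessarily enters the duration summary with a false value. The documents do not support that. An AESI whose recorded end month follows the last visit was still ongoing at that visit, and SAP 12.9.1 excludes AESIs ongoing at end of study. If ongoing status is judged from recorded data, the event drops out. If it is judged from the imputed date, the event looks resolved on the visit day and is counted. The SAP does not say which applies. Protocol Section 8.1.3 also has sites collect AESI duration directly, and how that relates to the date-based calculation is not stated.

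**Truncation at the visit may be intended.** That would be a defensible convention, but the SAP does not state it and specifies no matching cap for complete end dates.

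**Conclusion.** The point holds as a drafting error of minor consequence. On its literal terms, the end-date rule overrides a recorded month later than that of the last study visit and shortens the duration, by 1 to 61 days if the recorded month is the next calendar month. The shortening is usually a matter of weeks, but it can be a single day when the visit falls at month end.

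The effect is limited to listed AE durations and, depending on an unstated precedence, possibly the AESI duration summary. Efficacy results, TEAE incidence, sample size and alpha are untouched.

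Two broader readings should be resisted. A reader might infer that long events are shortened as a class. Only those with a missing end day and an end month after the visit month are. A reader might also want a percentage bias in mean duration. The documents give neither the frequency of such dates nor any durations, so any such figure would rest entirely on invented inputs.

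The conclusion assumes that some end dates after the last visit are recorded in this study's database, which the documents permit but do not confirm.

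**What to change.** In SAP Section 9, apply the end-date cap only when the recorded end month and year equal those of the last study visit, mirroring the condition on start dates. If the recorded month is later, keep the end-of-month imputation within that month. In SAP 12.9.1, state that an AESI whose recorded end month is after the last visit month counts as ongoing at end of study.

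If the sponsor does intend to truncate duration at the last visit, the SAP should say so and apply the cap to complete end dates as well.

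A minor drafting point can be settled at the same time: the definition of last study visit does not name subjects who withdraw early. Protocol Table 1 schedules both an early termination visit and a follow-up visit for them, so the SAP should say which visit is the anchor.

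The cost is a clause in Section 9, a sentence in 12.9.1 and one line of date-imputation code. No data collection changes.
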